15.2 Epworth Sleepiness Scale

Epworth Sleepiness Scale (ESS)

Name: _____ Today's date: _____

Your age (Yrs.): _____ Your gender (Male = M, Female = F): _____

How likely are you to doze off or fall asleep in the following situations, in contrast to just feeling tired?

This refers to your usual way of life recently.

Even if you have not done some of these things recently, try to figure out how they would have affected you.

Use the following scale to choose the **most appropriate number** for each situation:

- 0 = no chance of dozing
- 1 = **slight chance** of dozing
- 2 = **moderate chance** of dozing
- 3 = **high chance** of dozing

It is important that you answer each item as best you can.

Situation	Chance Of Dozing
Sitting and reading	
Watching TV	
Sitting inactive in a public place (e.g., a theater or a meeting)	
As a passenger in a car for an hour without a break	
Lying down to rest in the afternoon when circumstances permit	
Sitting and talking to someone	
Sitting quietly after a lunch without alcohol	
In a car or bus, while stopped for a few minutes in traffic	

THANK YOU FOR YOUR COOPERATION

© M.W. Johns 1990-1997

15.3 Assessment for Episodes of Sudden Onset of Sleep

Assessment for Episodes of Sudden Onset of Sleep

Definition of sudden onset of sleep: Abrupt episodes of unplanned sleep during activities of daily living where they are not expected to occur. These events may or may not be preceded by somnolence or sedation.

Instructions for the Screening Visit:

Did the subject experience any sudden onset of sleep in the last 6 weeks? (Check only 1 box)

- Yes, but the subject felt sleepy before (This is an indication of a possible sudden onset of sleep).
- Yes, subject fell asleep completely unexpected without prior sleepiness (This is an indication of a possible sudden onset of sleep).
- Yes, sometimes with, sometimes without prior sleepiness (This is an indication of a possible sudden onset of sleep).
- No

If the subject responds "Yes" to any of the above, the investigator should record the applicable response into the subject's Medical History. (e.g., "possible sudden onset of sleep")

Instructions for Visits After Screening:

Did the subject experience any sudden onset of sleep since the last visit? (Check only 1 box)

- Yes, but the subject felt sleepy before (This is an indication of a possible sudden onset of sleep).
- Yes, subject fell asleep completely unexpected without prior sleepiness (This is an indication of a possible sudden onset of sleep).
- Yes, sometimes with, sometimes without prior sleepiness (This is an indication of a possible sudden onset of sleep).
- No

If the subject responds "Yes" to any of the above (indicating a possible sudden onset of sleep), the investigator should evaluate if this is a change from Screening and if so report as an Adverse Event and determine whether the subject's continued participation in the study puts them at risk and whether they should be discontinued from the study.

15.4 Modified Minnesota Impulse Disorders Interview (mMIDI)

Modified Minnesota Impulse Disorders Interview (mMIDI)

Module 1: Buying Disorder Screen

Gateway Question:

Do you or others think that you have a problem with buying things too often or with spending too much money?

0 1
No Yes

If NO, go to the next module. If Yes, proceed with the following questions:

1. Do you ever experience an irresistible urge or uncontrollable need to buy things or mounting tension that can only be relieved by buying?

0 1 2 3
No Rarely Occasionally Frequently

2. Has problem buying led to social, marital, family, financial or work problems or caused you to experience significant distress?

0 1 2 3
No Rarely Occasionally Frequently

Module 1 score: _____ (add up all numbers, including gateway question)

Module 2: Compulsive Gambling Screen

Gateway Question:

Do you gamble?

0 1
No Yes

If NO, go to the next module. If Yes, proceed with the following questions:

1. Do you or others think that you have ever had a problem with gambling?
0 1 2 3
No Rarely Occasionally Frequently
2. Have you ever felt guilty about the way you gamble or what happens when you gamble?
0 1 2 3
No Rarely Occasionally Frequently
3. Have you been preoccupied with gambling or obtaining money to gamble?
0 1 2 3
No Rarely Occasionally Frequently
4. Have you gambled larger amounts of money or over longer periods of time than you intended to?
0 1 2 3
No Rarely Occasionally Frequently

Module 2 score: _____ (add up all numbers, including gateway question)

Module 3: Compulsive Sexual Behavior Screen

Gateway Question:

Do you or others that you know think that you have a problem with being overly preoccupied with some aspect of your sexuality or being overly sexually active?

- 0 1
No Yes

If NO, go to the next module. If Yes, proceed with the following questions:

1. Do you have repetitive sexual fantasies which you feel are out of your control or cause you distress?

- 0 1 2 3
No Rarely Occasionally Frequently

2. Do you have repetitive sexual urges which you feel are out of your control or cause you distress?

- 0 1 2 3
No Rarely Occasionally Frequently

3. Do you engage in repetitive sexual behavior which you feel is out of control or causes you distress?

- 0 1 2 3
No Rarely Occasionally Frequently

Module 3 score: _____ (add up all numbers, including gateway question)

Module 4: Compulsive Eating Module

Gateway Question:

Do you or others that you know think that you have a problem with being overly preoccupied with food or actively overeating?

- 0 1
No Yes

If NO, go to the next module. If Yes, proceed with the following questions:

1. Do you have repetitive fantasies about eating which are out of your control or cause you distress?

- 0 1 2 3
No Rarely Occasionally Frequently

2. Do you have repetitive urges to eat which you feel are out of your control or cause you distress?

- 0 1 2 3
No Rarely Occasionally Frequently

3. Do you engage in constant or overly frequent eating which you feel is out of control or causes you distress?

- 0 1 2 3
No Rarely Occasionally Frequently

Module 4 score: _____ (add up all numbers, including gateway question)

Module 5: Punding Behavior Screen

Gateway Question:

Do you find yourself fascinated with or performing repetitive and/or mechanical tasks such as taking apart and putting back together simple mechanical objects, or picking at oneself, or sorting and arranging common objects?

0 1
No Yes

If NO, end the module. If Yes, proceed with the following questions:

1. Do you collect things such as rocks, coins or books, and line them up together?
0 1 2 3
No Rarely Occasionally Frequently
2. Do you disassemble mechanical things such as doorknobs, watches, radios or other objects, and then re-assemble them?
0 1 2 3
No Rarely Occasionally Frequently
3. Do you find performing such repetitive tasks comforting?
0 1 2 3
No Rarely Occasionally Frequently
4. Do you get frustrated if you are unable to perform such repetitive tasks?
0 1 2 3
No Rarely Occasionally Frequently
5. Have you ever taken amphetamines?
0 1 2 3
No Rarely Occasionally Frequently

Module 5 score: _____ (add up all numbers, including gateway question)

SCORING:

The mMIDI consists of 5 modules: compulsive buying, compulsive gambling, compulsive eating, hypersexuality and punding.

Positive Answer:

Any answer other than “no” on any question is considered a “yes”/positive answer.

Negative Module:

A module is considered negative if the patient’s answer to a gateway (initial) question is “no” **or** if a patient answers “yes” to a gateway question and “no” to **all** of the remaining answers after the gateway question in that module.

Positive Module:

A module is considered positive if a patient gives a positive answer (rarely = 1, occasionally = 2, frequently = 3) to any question after the gateway (initial) question in one or more of the 5 modules.

During screening, if a subject has evidence of an impulse control disorder (ICD) (i.e., one or more positive modules on the mMIDI) the subject is ineligible for the study unless a structured clinical interview confirms that the subject does not have an ICD.

After administration of study drug, if a subject has one or more positive modules on the mMIDI, their continued participation in the study should be discussed with the Medical Monitor.

Total Score (add up all module scores): _____

Modules (Circle One Answer for Each Module: Positive or Negative):

- | | | |
|--|-----------------------------------|-----------------------------------|
| Module 1: Buying Disorder: |  Positive |  Negative |
| Module 2: Compulsive Gambling: |  Positive |  Negative |
| Module 3: Compulsive Sexual Behavior: |  Positive |  Negative |
| Module 4: Compulsive Eating: |  Positive |  Negative |
| Module 5: Punding Behavior: |  Positive |  Negative |

15.5 UK Parkinson's Disease Society Brain Bank Clinical Diagnostic Criteria

Step 1: Diagnosis of Parkinsonian syndrome

- Bradykinesia (slowness of initiation of voluntary movement with progressive reduction in speed and amplitude of repetitive actions)
- At least one of the following:
 - Muscular rigidity
 - 4-6 Hz rest tremor
 - Postural instability not caused by primary visual, vestibular, cerebellar, or proprioceptive dysfunction.

Step 2: Exclusion criteria for Parkinson's disease

- History of repeated strokes with stepwise progression of Parkinsonian features
- History of repeated head injury
- History of definite encephalitis
- Oculogyric crises
- Neuroleptic treatment at onset of symptoms
- More than one affected relative
- Sustained remission
- Strictly unilateral features after 3 years
- Supranuclear gaze palsy
- Cerebellar signs
- Early severe autonomic involvement
- Early severe dementia with disturbances of memory, language, and praxis
- Babinski sign
- Presence of cerebral tumor or communicating hydrocephalus on CT scan
- Negative response to large doses of levodopa (if malabsorption excluded)
- MPTP exposure

Step 3: Supportive prospective positive criteria for Parkinson's disease

(Three or more required for diagnosis of definite Parkinson's disease)

- Unilateral onset
- Rest tremor present
- Progressive disorder
- Persistent asymmetry affecting side of onset most
- Excellent response (70-100%) to levodopa
- Severe levodopa-induced chorea
- Levodopa response for 5 years or more
- Clinical course of 10 years or more

15.6 Modified Hoehn and Yahr

Modified Hoehn and Yahr PD Staging

The Modified Hoehn and Yahr PD Staging is a scale expressing the severity of the symptoms of PD. It provides a practical classification of 5 stages of ever increasing severity. The stages are defined as:

Stage 0	=	No signs of disease.
Stage 1	=	Unilateral disease.
Stage 1.5	=	Unilateral plus axial involvement.
Stage 2	=	Bilateral disease, without impairment of balance.
Stage 2.5	=	Mild bilateral disease, with recovery on pull test.
Stage 3	=	Mild to moderate bilateral disease; some postural instability; physically independent.
Stage 4	=	Severe disability; still able to walk or stand unassisted
Stage 5	=	Wheelchair bound or bedridden unless aided.

Hoehn MM, Yahr MD (1967). Parkinsonism: onset, progression and mortality. *Neurology*. **17**(5):427-42.

15.7

[Redacted text block]

- | [Redacted list item]
- | [Redacted list item]
- | [Redacted list item]
- [Redacted list item]
- | [Redacted list item]
- | [Redacted list item]
- | [Redacted list item]

[Redacted text block]

- [Redacted list item]
- | [Redacted list item]
- | [Redacted list item]
- | [Redacted list item]

15.8 Fall Questionnaire

Fall Questionnaire

Baseline (Visit 2):

Have you been experiencing falls over the past 3 months? Yes/No

If yes, approximately how many falls have occurred in the past 3 months? _____

At Week 24 (Visit 6) and Week 52 (Visit 8):

Have you been experiencing falls over the past 3 months? Yes/No

If yes, approximately how many falls have occurred in the past 3 months? _____

In the event of an Early Termination Visit:

Have you been experiencing falls over the past 3 months? Yes/No

If yes, approximately how many falls have occurred in the past 3 months? _____

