3.1.1 Study Duration Per Patient

Each patient will participate for up to 62 weeks, which includes a Screening Period of 1 to ≤ 6 weeks, followed by a Baseline Visit, 52 weeks of open-label treatment, and a Safety Follow-Up Visit 4 weeks after completion of investigational treatment:

- Screening Period: 1 to ≤ 6 weeks.
- Open-Label Treatment Period: 52 weeks.
- Post-Treatment Safety Follow-Up: 4 weeks.

The total anticipated study duration for an individual patient will be a minimum of 57 weeks and a maximum of 62 weeks. The end of the study is defined as the date of the last visit of the last patient in the study.

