6.2.3.4 Assignment and Dispensing of Investigational Medicinal Product

Note: Sites participating in Expanded PK Sampling should refer to [Appendix 15.9.1](#) for Assignment and Dispensing of IMP instructions.

1. For patients meeting all entry criteria, complete the IMP assignment transaction using the IXRS by following the procedures provided.
 - a. Dispense the open-label IMP bottle(s) assigned by the IXRS to the patient for this study visit. Each bottle consists of either 50 tablets of 120 mg tozadenant or 100 tablets of 60 mg tozadenant.
 - b. Record the date IMP was dispensed in IMP dispensing records including patient number, assigned IMP bottle number(s), and date and time IMP was dispensed.
 - c. Review the dosing instructions for the IMP with the patient, answer any questions, and remind the patient to return the IMP (including all used, unused and partially used bottles) at the next visit.
 - d. Patients will be instructed to take either two (2) 60 mg tablets or one (1) 120 mg tablet of the dispensed IMP by mouth BID, in the morning and in the evening preferably at the same time each day, for a total of either two (2) 120 mg tablets or four (4) 60 mg tablets per day. The evening dose should be approximately 12 hours after the morning dose. Patients will be instructed to take their morning and evening doses 1 hour before or 2 hours after a meal and to refrain from eating for 1 hour after dosing. Patients should take the first dose of IMP at home after the Baseline Visit.
2. Instruct the patient to take the first dose of IMP at home on the evening of dispensation.
3. Ensure that the patient understood the dosing instructions and the use of the extra doses included in the bottle if visit delayed and/or use of visit window.
4. Schedule the Week 2 visit. If needed, use the visit window in relation to the date of the Baseline visit.

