7.3 Fall Questionnaire

A Fall Questionnaire will be utilized to solicit information about patient falls, defined as coming to rest on the ground inadvertently from a standing position, during this study. The assessment will ask if a patient has been experiencing falls over the past 3 months, and if so, approximately how many falls have occurred during that interval.

An example of the Fall Questionnaire is provided in [Appendix 15.8](#).

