9.6.1. Exploratory Variables

The exploratory variables including the change from Baseline (where applicable) will be summarized using descriptive statistics by visit:

1. UPDRS Part II (ADL subscale) + Part III (motor subscale) total score
2. UPDRS Part II (ADL subscale) score
3. UPDRS Part III (motor subscale) score in the ON state
4. UPDRS Part I total score
5. UPDRS Part IV total score
6. Dyskinesia as measured by questions 32, 33 and 34 of UPDRS Part IV
7. Motor fluctuations as measured by question 39 of UPDRS Part IV
8. Clinical Global Impression of Improvement (CGI-I)
9. Patient's Global Impression of Improvement (PGI-I)
10. Parkinson's Disease Quality of Life Questionnaire (PDQ-39; total score and individual domain scores)
11. Non-motor Symptom Assessment Scale
12. Patient-completed diaries (Change from Baseline in the number of hours per day spent as follows: OFF, ON time without troublesome dyskinesia, total ON time, ON time with troublesome dyskinesia and asleep time)
13. Healthcare Resource Utilization
14. EuroQol 5D-5L Health Questionnaire (EQ-5D-5L)
15. Fall questionnaire

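### At an Early Termination visit before about Week 13, the Fall Questionnaire's fixed 3-month recall reaches back before the first dose and dilutes the change from Baseline

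*Protocol*

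**What the plan says.** Protocol 7.3 introduces the Fall Questionnaire as a way to gather information on falls in the study and then fixes the recall: "The assessment will ask if a patient has been experiencing falls over the past 3 months". Appendix 15.8 gives the wording. Each administration asks "Have you been experiencing falls over the past 3 months? Yes/No" and then "If yes, approximately how many falls have occurred in the past 3 months". The blocks for Baseline, for Weeks 24 and 52, and for ET ("In the event of an Early Termination Visit") are identical. The ET block has no limit at first dose. Table 1 agrees with this schedule, and no other visit carries the form.

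On the start of treatment, Protocol 6.2.3.4 states: "Patients should take the first dose of IMP at home after the Baseline Visit". The Baseline recall is therefore wholly pre-treatment.

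The questionnaire is listed among the other endpoints (Protocol 2.2.2 and 11.2.3), not the safety endpoints. SAP 9.6.1 includes it in a list introduced by: "The exploratory variables including the change from Baseline (where applicable) will be summarized using descriptive statistics by visit". SAP section 9 lets ET data count toward a scheduled week if the visit falls in that week's window. Otherwise the data go into a separate ET column. Neither document adjusts for the length of recall that falls on treatment.

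**The concern.** A fixed look-back works when every administration is at least that long after the first dose. An early ET visit is not. A patient who stops at Week 4 is asked about 13 weeks, of which 9 precede the first dose. Those 9 weeks were already reported at Baseline. The same falls can enter both counts, and the difference between them understates whatever happened on drug.

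This matters because, for anyone who stops before Week 24, the ET form is the only post-baseline fall count this instrument provides. A near-zero change in the ET column could be read as no effect on falls among early stoppers when it is largely an artefact of the window.

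**Working it through.** **Inputs.** Recall of 3 months, taken as 91 days or 13 weeks (Appendix 15.8; 84 to 92 days tested). First dose after the Baseline Visit (Protocol 6.2.3.4). "Open-Label Treatment Period: 52 weeks" (Protocol 3.1.1). Visit windows of ±7 days at Week 24 and ±14 days at Week 52 (Table 1). The documents state no coverage figure to reproduce.

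**1. Pre-treatment share at ET.** For an ET visit at week t, taken as t weeks after first dose, the share is (13 − t)/13 for t below 13, and zero after that. The same days lie inside the Baseline window.

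| ET week | Pre-treatment days of 91 | Share | Range, 84 to 92 days |
|---|---|---|---|
| 2 | 77 | 85% | 83–85% |
| 4 | 63 | 69% | 67–70% |
| 6 | 49 | 54% | 50–54% |
| 8 | 35 | 38% | 33–39% |
| 12 | 7 | 8% | 0–9% |
| 13 | 0 | 0% | 0–1% |

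**2. Effect on the change from Baseline.** Let the pre-treatment rate be r falls per week and the on-treatment rate k·r, both constant.

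- Baseline count: 13r.
- ET count: (13 − t)r + t·k·r.
- Observed change: t(k − 1)r.
- Change that a full on-treatment window would show: 13(k − 1)r.

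The fraction retained is t/13 whatever k is: 15%, 31%, 46% and 62% at Weeks 2, 4, 6 and 8. As an illustration with k = 2, the apparent ratio is (13 + t)/13 = 1.15, 1.31, 1.46 and 1.62, against a true 2.0. The doubling is assumed, not taken from the documents.

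**3. Where the diluted values go.** The earliest Week 24 visit is day 168 − 7 = 161, and its recall starts at day 161 − 91 = 70. The earliest Week 52 visit is day 364 − 14 = 350. An ET visit before day 91 cannot fall in either window. Its count goes to the ET column or, if the SAP rule is applied literally, to a Week 2, 6 or 12 summary for which no continuing patient is asked.

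**4. Coverage of the scheduled form.** Week 24 covers Weeks 11–24 and Week 52 covers Weeks 39–52, together 26 of 52 weeks. Weeks 0–11 (11 weeks) and 24–39 (15 weeks) are not asked about: 26/52 = 50%. The uncovered share runs from 49.5% to 53.8% for a recall of 92 to 84 days, and from 48% to 52% across the visit windows.

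**5. After the fix.** With recall capped at first dose, an ET visit at Week 4 covers 4 weeks and no pre-treatment days. With k = 2 the rate is (4 × 2r)/4 = 2r, against 13r/13 = r at Baseline, so the ratio is 2.0.

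**The case against.** The strongest reply is that the snapshot is the stated design. Protocol 7.3 sets the 3-month recall explicitly, for an endpoint that describes PD status and is summarised without any test. Equal windows make Baseline, Week 24 and Week 52 directly comparable. That stands.

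From the 50% figure a reader might infer that half the treatment year goes unmonitored for falls, or that the endpoint cannot characterise falls at all. The documents do not support this. Adverse events are prompted at the scheduled clinic visits (Protocol 9.1.2), UPDRS items 13 and 14 rate falling and falls from freezing over the past week, and hospital and emergency visits are recorded with reasons. None of these gives a comparable 3-month count, and the adverse event prompt is open-ended, so capture is partial. It is not absent.

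A reader might also infer that the early ET counts contaminate the main by-visit results, or that the plan labels pre-treatment falls as on-treatment. Step 3 rules out the first for Weeks 24 and 52. As to the second, the documents use no such label. The problem is only that the ET count is reported as post-baseline without truncation.

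Two uncertainties remain. The documents give no rate of ET before Week 13, so the number of patients affected is unknown. Protocol 6.2.20 also skips efficacy-related measures at ET when drug stopped more than 24 hours earlier. Whether that covers this form is left open, and if it does, fewer affected records would exist.

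**Conclusion.** The point holds for ET visits within about 13 weeks of first dose. There the recall overlaps the Baseline window by roughly 38% to 85% at Weeks 8 to 2, and only t/13 of any true change in fall count is retained. The bias is toward no change and is confined to summaries of ET data. Week 24 and Week 52 summaries, the safety endpoints and the sample size are unaffected.

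The size rests on a 13-week recall, constant rates before and after first dose, accurate recall, and an ET visit close to the last dose. The overlap itself needs only the recall length and the visit date.

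The half-year gap is arithmetically right for this instrument, but it is a limit on what the measure describes, not an error in the scheduled comparisons. It calls for accurate labelling. Continuous capture would be a preference.

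**What to change.** - **Appendix 15.8, ET block:** ask about falls *since the first dose of IMP, or over the past 3 months, whichever is shorter*, and record the length of that interval.
- **SAP 9.6.1:** report falls per patient-month of recall, so that a 4-week ET window and a 13-week Baseline window are on the same scale. Once the recall is capped, no further exclusion is needed.
- **If the form cannot be changed:** flag ET visits within 3 months of first dose and leave them out of the change-from-Baseline fall summary. This drops those early stoppers from that summary, so it is second best.
- **Protocol 7.3 and the study report:** describe the scheduled measure as a 3-month snapshot at Weeks 24 and 52, not as falls over the whole study.
- **Optional:** add the two questions at the existing Week 12 and Week 36 visits. Coverage becomes Weeks 0–36 and 39–52, or 49 of 52 weeks. If Weeks 24 and 36 keep a 3-month recall, adjacent windows overlap by about one week (11–12 and 23–24), so counts should not be summed across visits.

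Cost: the wording change needs a protocol amendment with its approvals (Protocol 12.4) and a revised form with one added field at about 120 sites. The SAP changes and the fallback flag use dates already collected and cost sites nothing.
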